- Children and adolescents with skeletal fragility due to genetic causes;
- Children and adolescents who chronically use drugs capable of altering lipid metabolism and bone remodeling;
- Children and adolescents placed on a diet-therapeutic regimen with dietary styles other than the Mediterranean or Western diet (e.g., ketogenic diet, FoodMap diet, vegan/vegetarian diet) to avoid bias in the interpretation of the microbial signature (the microbial signature of the Western and Mediterranean diets is known in the literature);
- Failure of parents or adolescent (from age 12 years) to give informed consent;

Surgery

No type of surgery

DURATION OF THE STUDY

12-month recruitment and 12-month observation period for sociological survey.

SCDU di Endocrinologia

AOU Maggiore della Carità, [name]

[contact] (Reparto); [contact]

[contact]

Timing of data collection

At the time of recruitment, patients afferent at the Outpatient Endocrinology Clinic of the AOU Maggiore della Carità in Novara, at the Transition Endocrinology Outpatient Clinic of the Endocrinology SCDU, and at the "B. Trambusti" Pediatric Endocrinology Outpatient Clinic of the Giovanni XXIII Children's Hospital will undergo:

Questionnaires to assess the amount of fructose introduced in the diet:

- Questionnaire to assess adherence to the Mediterranean diet in children/adolescents, KIDMED;
- Questionnaire to assess food frequency in children, IDEFICS;
- 24h recall questionnaire, to collect information regarding meals taken in the previous 24 hours. The amount of macronutrients will be obtained through dedicated software "Dietosystem Professional Food Therapy Software" from DSMedica. The questionnaire is added with specific questions and figures to identify the portions of foods and put them in relation to the amount of fructose intake;
- Calculation of the Dietary Inflammatory Index (DII) using a list of foods. This parameter makes it possible to define the extent to which a dietary pattern is able to promote the synthesis of pro-inflammatory molecules (17,18);
- Sociological questionnaire prepared ad hoc by Unit 3 to assess diet and fructose intake in relation to family socioeconomic status.

Anamnestic evaluation

- The patient's mother will be asked about the gestational age, mode of delivery and anthropometric data of the child at birth.
- Detection of current drug therapy (if any).

Instrumental assessment

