Descriptive statistics will be calculated in order to summarize the sociodemographic, perceptual, anthropometric, dietary, clinic-auxological, anamnestic and laboratory characteristics of the children included in the study.

Categorical variables will be summarized by absolute frequencies and percentages while numerical variables as mean and standard deviation (SD) or median and interquartile range (Q1-Q3) if not normally distributed according to the Shapiro Wilks test and quantile plot observation. The chi-square test or the corresponding nonparametric Fisher's test will be used to test the association between categorical variables and the presence of NAFLD while the t-test or the Mann-Whitney test will be used to test the difference in fructose consumption between children with NAFLD and those without the disease as well as the presence of differences between the two groups for the other numerical variables. The positive false discovery rate method will be used to account for the presence of multiple tests. Based on the number of NAFLD events observed, stratified analysis by age group (preschool age vs. adolescents) and center will be evaluated. **Regarding the assessment of bone metabolism, mean and standard deviation (SD) or median and interquartile range (Q1-Q3) of the parameters provided by the QUS overall and separately for high and low fructose consumption (below vs above median consumption) will be calculated.**

Microbiota analysis

Initially, an exploratory analysis of the relative abundance of the genera of bacteria in the microbiota will be carried out. The relative abundance of each species detected in the fecal samples will be represented by heatmaps. Next, a beta-diversity analysis will be performed comparing the complexity of genera

between subjects. Specifically, three matrices will be created based on weighted and unweighted Bray-Curtis and Unifrac distances that will be used to perform a principal coordinate analysis to highlight the presence of subject clusters based on the complexity of their microbiota.

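### The bone analysis splits all children at one pooled fructose median, apparently from a single-day recall, so the high and low groups are blurred and can partly reflect age

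*Combined protocol and SAP*

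**What the plan says.** Under Timing of data collection, five dietary tools are listed beneath the heading "Questionnaires to assess the amount of fructose introduced in the diet". They are KIDMED, the food-frequency tool ("Questionnaire to assess food frequency in children, IDEFICS"), the 24-hour recall ("24h recall questionnaire, to collect information regarding meals taken in the previous 24 hours"), a food list for the Dietary Inflammatory Index, and a sociological questionnaire. Only the recall is given nutrient software and portion aids, with "figures to identify the portions of foods and put them in relation to the amount of fructose intake". The tools are administered once ("At the time of recruitment, patients afferent at the Outpatient Endocrinology Clinic"). No second recall is described, and the 12-month observation period is for the sociological survey.

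The Statistical analysis section uses a fructose variable twice. A t-test or Mann-Whitney test is "used to test the difference in fructose consumption between children with NAFLD and those without the disease". The bone ultrasound (QUS) parameters are summarised by mean and SD, or median and quartiles, overall and by a split at median consumption. No test is planned for the bone split. The section does not say which instrument supplies fructose consumption, how the tools are combined, or how day-to-day variation is handled.

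The Inclusion criteria admit two separate age bands, 3 to 6 and 12 to 16 years. Stratification by age group and centre is mentioned only as something to be considered, depending on the number of NAFLD events. It is not attached to the bone summaries.

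**The concern.** The aims concern the effects of fructose intake on liver complications and bone metabolism, and relate the omics findings to dietary habits. These are questions about usual intake. Two features weaken the bone analysis as an answer.

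- **Noise.** One day's grams equal usual intake plus that day's deviation. A median cut on a noisy variable mixes the two groups and shrinks the contrast between them, so a flat result could mean no relation or a poorly measured exposure.
- **Age.** A single cut in grams across preschoolers and adolescents tends to place more adolescents in the high group if they consume more grams. Bone ultrasound values may also differ with age. The contrast then partly compares older with younger children, and nothing in the plan separates the two.

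The first problem hides a true relation. The second can create an apparent one.

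**Working it through.** **1. The plan's own figure.** Inputs from Sample size and statistical methods: 100 children at 1:3 (25 with NAFLD, 75 without), variance 9.53, alpha 0.05 (taken as two-sided), power 80%.

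- SD = √9.53 = 3.087 g.
- Standard error = 3.087 × √(1/25 + 1/75) = 0.713 g.
- Detectable difference: normal approximation (1.960 + 0.842) × 0.713 = 1.997 g; noncentral t 2.017 g.

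The stated 2.02 g reproduces.

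**2. Misplacement at the median.** The documents do not give the ratio λ of within-child to between-child variance, so it is an assumption. Suppose one-day intake is usual intake plus independent normal error, either in grams or on the log scale. The correlation of one day with usual intake is then ρ = 1/√(1+λ), and the share on the wrong side of the median is arccos(ρ)/π. A high-low contrast in a linearly related bone parameter keeps a fraction ρ of its size.

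| λ (assumed) | ρ = contrast kept | wrong side of median |
|---|---|---|
| 0.5 | 0.82 | 19.6% |
| 1 | 0.71 | 25.0% |
| 2 | 0.58 | 30.4% |
| 3 | 0.50 | 33.3% |

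Simulation with 100 children and the sample median agrees (19.9%, 25.2%, 30.3%, 33.5%). If the two age bands differ by an assumed 1 SD in usual intake, the extra spread lowers the figures slightly, to 17.9%, 23.3%, 28.7% and 31.8%.

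**3. Age in the pooled split.** Assume equal numbers in the two age bands, recorded intake d SD higher in adolescents, bone values 1 SD higher in adolescents, and no effect of fructose (SDs within age band). The pooled median lies midway between the bands, so a share Φ(d/2) of the high group and 1 − Φ(d/2) of the low group are adolescents. The high-low bone difference is [2Φ(d/2) − 1] × 1 SD.

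- d = 0.25: 2 × 0.550 − 1 = 0.10 SD.
- d = 0.5: 2 × 0.599 − 1 = 0.20 SD.
- d = 1: 2 × 0.691 − 1 = 0.38 SD.

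Splitting at the median within each band makes the age mix equal and removes this term.

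**4. Cost of the split itself.** Assume a true correlation of 0.4 between usual intake and a bone parameter, and n = 100. The observed correlation is r = 0.4ρ with continuous grams. With a median split it is multiplied by √(2/π) = 0.798. Power ≈ Φ(atanh(r) × √97 − 1.96).

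- λ = 1: r = 0.283 gives 82%; split, r = 0.226 gives 62%.
- λ = 3: r = 0.200 gives 51%; split, r = 0.160 gives 35%.

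No bone test is planned, so these figures only show how much information the cut discards.

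**5. Could the food-frequency data replace the recall?** Predicting recall grams from food-frequency answers drops each child's own recall. If those answers correlate 0.5 with usual intake (assumed), misplacement is arccos(0.5)/π = 33%, against 25% to 33% for the raw recall at λ = 1 to 3. In simulation at λ = 1, power is about 52% with the prediction, against about 82% with the recall. Calibration can correct an attenuated slope, provided errors in the two tools are independent, but it does not sort children better.

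**The case against.** The strongest reply is that the plan never says the median comes from the recall. The food-frequency tool stands under the same fructose heading, dietary characteristics are to be summarised, and numerical variables are to be compared by NAFLD status. This stands. The recall as source is an inference, though the best supported one, because no other tool is tied to portions and grams. A reader might go further and infer that the food-frequency data go unused. The documents do not support that; they only leave open whether those data help to derive fructose grams.

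Second, the size of the misplacement rests on a variance ratio that the documents do not give, so the percentages are illustrations over a range. This also stands.

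Third, the bone split is descriptive and matches an aim to describe. So the harm is a diluted or age-mixed description, not a false test result. The age problem remains, because a descriptive contrast will still be read as a fructose contrast.

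A reader might also infer that the NAFLD comparison is underpowered and that 2.02 g is wrong. The documents do not support this. The figure reproduces, and they do not say whether the variance of 9.53 describes one-day or habitual intake. If it already contains day-to-day variation, no power is lost. Random day-to-day error also does not bias the difference in mean grams between children with and without NAFLD.

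**Conclusion.** The point holds as a limited weakness in how the exposure is defined and used. The text firmly shows that one tool is tied to an amount of fructose, that it is given at recruitment with no repeat described, that the source of the analysed variable is not named, and that one pooled median is used across two distant age bands.

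If the recall is the source, about 20% to 33% of children are misplaced for an assumed variance ratio of 0.5 to 3, and a linear high-low contrast keeps 82% to 50% of its size. Independently of that noise, the pooled cut can produce a bone difference of about 0.1 to 0.4 SD from age alone. That range rests on the assumed age differences in recorded intake and bone values and on equal age bands; it is smaller if those differences are smaller. The planned sample size is not called into question.

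**What to change.** In the Statistical analysis section:

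1. Name the 24-hour recall as the source of fructose grams, and describe all results based on it, including the NAFLD comparison of means, as one-day intake.
2. Relate each QUS parameter to fructose grams as a continuous variable, adjusted for age (or age group), sex and centre.
3. If high and low groups are kept for description, split at the median within each age group.
4. Optionally, add a sensitivity analysis calibrated on the IDEFICS frequencies, with the same covariates in the outcome model and the weekday of the recall recorded and standardised. It should not replace the recall, and no reduction in misclassification should be claimed for it.

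The first three items need only changes of wording and a little more analysis, with no new data and no change to the sample size. The price is an assumed linear form for the continuous model, which should be checked by plotting. Noise from a single day remains, so the limitation must still be stated.

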Reduced phosphate uptake, on the other hand, depends on the depletion of phosphate groups by a specific isoform of phosphofructokinase expressed by enterocytes (13); therefore, the reduction in the ATP/AMP ratio leads to inhibition of the Na/P transporter. This mechanism would also occur at the renal level where inhibition of this transporter promotes urinary excretion of phosphorus (14).

Recent studies show how an increase in dietary fructose appears to be responsible for the onset of several obesity-associated diseases; foremost among them NAFLD, which is increasing in tandem with obesity even in the pediatric population. The aim of this study is mainly to understand the effect of fructose on the molecular events contributing to pediatric development, as this could be an important target to address the clinical and social problems arising from its prevalence in pediatric age.

AIMS OF THE STUDY

The primary aim of this study is to evaluate the effects of fructose intake in a group of preschool children and overweight or obese adolescents; in particular, to investigate the impact of fructose consumption in the development of liver complications, such as NAFLD, and its degree of severity, as well as its impact in other obesity-associated diseases. **In addition, the present study aims to describe the composition of bone metabolism according to the level of fructose consumption.** Secondly, by means of omics analysis (metabolomics and metaproteomic), the aim is to characterize the microorganisms present in the gastrointestinal tract and their microbial activity in relation to dietary habits, fructose intake and clinical parameters. Finally, sociodemographic and cultural factors, in the children and adolescents considered in the study, and in their families, will be surveyed.

STUDY DESIGN

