- Quantitative and qualitative analysis of bone composition using quantitative ultrasonography (QUS). This instrument provides different parameters related to bone composition, specifically speed of sound (SOS) assessing bone density, broadband ultrasound attenuation (BUA) assessing trabecular structure, ultrasound peak amplitude assessing trabecular size, number of peaks assessing connectivity of the mineralized matrix structure, and fast wave energy and amplitude assessing elasticity.
- US ultrasound of the abdomen to evaluate hepatic steatosis, perivisceral and subcutaneous fat. The presence of hepatic steatosis (NAFLD) will be classified from stage 1 to stage 3 according to literature (19).

Clinic-auxological evaluation

- Anthropometric measurements, such as weight, height and BMI assessment according to STANDARD DEVIATION SCORE (SDS). Waist and hip circumference measurements.
- Measurement of blood pressure and heart rate.
- Analysis of body composition by bio-impedance analysis (BIA)

Laboratory evaluation, hematochemical assays

Subjects will undergo the following assessments after at least 12 hours of overnight fasting:

- OGTT (glucose-loading curve; glucose 1.75 g/kg per os at time 0', maximum dose 75 g), with basal and every 30 min blood glucose and insulin draws.
- Basal blood draw for c-peptide, AST, ALT, gamma-GT, fractional and total bilirubin, azotemia, creatinine, eGFR, HbAic, fructosamine, total cholesterol, HDL, triglycerides, TSH, FT3 and FT4, leptin, adiponectin, DPP4, uric acid.
- Basal blood sampling for PCR, advanced glycation products (AGEs), AGE receptor (RAGE) and advanced protein oxidation products (AOPPs),
- Basal blood sampling for assay of intermediate products of fructose metabolism (fructose-lysine)
- Calcium, phosphorus, 25-OH vitamin D, PTH, osteocalcin, RANKL, osteoprotegerin, bone isoenzyme alkaline phosphatase, telopeptide C-terminal collagen type I (CTX), intact procollagen amino terminal type 1 (P1NP), IL-6, IL-1beta, biochemical parameters needed to assess bone metabolism.

They will, in addition, be performed:

- A urinalysis and 24-hour urine collection for evaluation of fructose metabolites in urine.
- Fecal sample for metabolomics and metaproteomic analysis.

ANALYSIS BY BIOCHEMICAL, HORMONAL AND MASS SPECTROMETRY PARAMETERS

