Biochemical parameters according to clinical practice will be analyzed at the laboratories of Maggiore della Carità Hospital in Novara and at the laboratories of Giovanni XXIII Children's Hospital in Bari by estimation with Siemens Advia 2400 Healthcare Diagnostics, Siemens ADVIA chemistry XPT and in accordance with the respective protocols of reagent use.

Metaproteomic and metabolomics analysis will be conducted on stool, plasma and urine samples stored during the study for omics signature designation. Metaproteomic analysis with UPHLC-MS/MS mass spectrophotometer will be performed on stool samples to identify the presence of microorganisms in the gastrointestinal tract to be then correlated with the diet followed and clinical parameters of the patients. Peptides identified by the analysis will be entered into the UniProtKB, KEGG database and used for phylogenetic analysis.

Metabolomic analysis will be carried out on all three types of samples; metabolomics conducted on fecal samples will allow assessment of the functional activity of microorganisms, characterizing the intermediate phenotype that mediates host-microbiome interactions. Using one-dimensional gas chromatograph coupled with mass spectrometer (GC-MS-SPME), the metabolic profile and changes in metabolite levels in association with fructose intake will be identified. The identification of the main SCFAs will be carried out with the same instrument and then confirmed by injecting the appropriately treated samples into the instrument, comparing the retention time and the corresponding spectra obtained from GC-MS analysis. This method allows a metabolomic signature to be defined in relation to fructose consumption.

SAMPLE SIZE AND STATISTICAL METHODS

The study plans to enroll 100 children afferent to the centers previously listed. Given a first-type error of 0.05, a power of 80%, a variance of equal fructose consumption in the groups of children with and without NAFLD of 9.53 (pooled variance obtained from data reported in the article by Nier et al. (20), a ratio of 1:3 between children with and without NAFLD (expected prevalence in overweight and obese children ~24% (21)), the sample size will allow to highlight as statistically significant a minimal difference in the averages of fructose consumption between healthy and diseased children of 2.02 grams.

Statistical analysis

Evaluation of the relationship between fructose and NAFLD

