The “Linear discriminant analysis effect size” (LEFSE) method will be used to identify taxa that best discriminate between NAFLD-infected and non-infected patients. The LefSE method is an algorithm-based approach that performs the nonparametric Kruskal-Wallis and Wilcoxon rank-sum test to identify bacterial taxa whose relative abundance is statistically different between groups. Then discriminant analysis is applied considering only those bacterial taxa found to be significantly different between the two groups.

EXPECTED RESULTS

The present study is expected to gain new knowledge on the effect of fructose in relation to the onset of obesity-associated liver disease (NAFLD) and bone metabolism, with the identification of new biological, immunological, and omics markers that can be studied in the future as disease targets in the pediatric population. In addition, due to the scientific and sociological interest, the present study aims at the identification of sociodemographic and cultural determinants related to fructose intake, useful for the creation of preventive campaigns aimed at the promotion of a healthy lifestyle, with a change in eating habits that incentivize a healthy diet and a reduction of obesity status in the population. The results obtained, if statistically significant, will ultimately aim to develop effective preventive communication to promote a healthier lifestyle and diet in the population.

ETHICAL ASPECTS

The study was designed and will be conducted in accordance with international and national ethical standards on biomedical research with human beings, specifically:

- *Ethical principles for medical research involving human subjects* (Declaration of Helsinki -World Medical Association, current version);
- European Union *Standards of Good Clinical Practice* (ICH/GCP);
- *Convention on Human Rights and Biomedicine* (Oviedo Convention of 04/04/1997);
- Italian codes of ethics for health professions and specific current national regulations on clinical trials.

Management of informed consent

An information sheet explaining the type of study, purpose, procedures, sample and data collection, and possible benefits and risks of the research is available. This information will be presented to interested persons, who will have the freedom to give consent or to be able to withdraw it when the study has already begun.

Management of sensitive data

The following European and national regulations are kept in mind:

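### Past antibiotic and probiotic use is neither restricted nor recorded before stool sampling, so recently exposed children cannot be identified in the secondary omics analyses

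*Combined protocol and SAP*

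**What the plan says.** - **Aim.** Under Aims of the Study, the second aim is omics-based and links stool findings to diet and to clinical measurements: "the aim is to characterize the microorganisms present in the gastrointestinal tract and their microbial activity in relation to dietary habits, fructose intake and clinical" (…).
- **Eligibility.** The Exclusion criteria remove children on certain diets "to avoid bias in the interpretation of the microbial signature". The only drug-related exclusion is "Children and adolescents who chronically use drugs capable of altering lipid metabolism and bone remodeling". A short antibiotic course or a probiotic does not fall under it.
- **History.** Under Timing of data collection, the Anamnestic evaluation has two items: birth data, and "Detection of current drug therapy (if any"). The drug item has no look-back period and does not name antibiotics or probiotics.
- **Sampling.** The Laboratory evaluation lists a "Fecal sample for metabolomics and metaproteomic analysis", attaching no condition about recent medication. The assessments are set at recruitment.
- **Analysis.** The Microbiota analysis section plans heatmaps, beta-diversity with principal coordinate analysis, and LEfSe, a "method will be used to identify taxa that best discriminate between NAFLD-infected and non-infected patients". It names no exclusion, covariate or sensitivity analysis for drug exposure. Stratification appears only in the fructose–NAFLD section, where, depending on the number of NAFLD events, "stratified analysis by age group (preschool age vs. adolescents) and center will be evaluated".

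**The concern.** The protocol accepts that the microbial signature needs protection from outside influences, and guards against one of them, unusual diets. Recent antibiotics and probiotics are another plausible influence on stool bacteria and their metabolites, and the plan neither limits nor records them once they have been stopped.

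For example, a preschool child who finished an antibiotic course the week before recruitment is eligible, gives stool, and is recorded as taking nothing. At analysis that child looks the same as an unexposed one. If such children are spread evenly over the groups, they add noise. If they are more common in one NAFLD group, or at one level of fructose intake, part of an observed difference may come from the medication. Without a record of past use, the study team cannot count these children or show that the results hold without them.

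**Working it through.** **1. The plan's own figure.** The only powered quantity is the detectable difference in fructose consumption: variance 9.53 (SD 3.087 g), 100 children at 1:3 (25 with NAFLD, 75 without), alpha 0.05, power 80%.

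- Two-sided t calculation: 2.017 g, which agrees with the stated 2.02 g.
- Normal approximation: 2.80 × 3.087 × √(1/25 + 1/75) = 2.80 × 3.087 × 0.231 ≈ 2.00 g.

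Stool data do not enter this calculation, so the point leaves it untouched.

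**2. What the record can show.**

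| Exposure before stool sampling | Excluded? | Recorded? |
|---|---|---|
| Antibiotic still being taken at recruitment | No | Yes, as current therapy |
| Antibiotic course already completed | No | No |
| Probiotic counted as therapy, current | No | Yes |
| Probiotic not counted as therapy, or stopped | No | No |

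The food-frequency and 24-hour recall questionnaires might pick up some probiotic foods, but the plan does not say so. The gap is rows two and four.

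**3. Noise, on assumed inputs.** The documents give neither the exposed fraction f nor the shift δ (in SD units) in an affected feature. Take f = 10–30% and δ = 0.5–1.5, spread equally over the groups. Variance inflation is 1 + f(1 − f)δ².

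| f | δ | Inflation | 100 samples act like |
|---|---|---|---|
| 0.10 | 0.5 | 1 + 0.09 × 0.25 = 1.02 | 98 |
| 0.20 | 1.5 | 1 + 0.16 × 2.25 = 1.36 | 74 |
| 0.30 | 1.5 | 1 + 0.21 × 2.25 = 1.47 | 68 |

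For 25 versus 75 children, the detectable standardised difference is 2.80 × 0.231 = 0.65 SD before any multiplicity correction. Power at that difference falls from 80% to 79.1%, 67.1% and 63.6% in the three rows.

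**4. Bias through age, on assumed inputs.** Take equal age bands, recent use of 25% in preschool children and 8% in adolescents, and NAFLD in 10% and 38% (average 24%, matching the plan's expected prevalence).

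- Exposed among NAFLD: (0.10 × 0.25 + 0.38 × 0.08) / 0.48 = 11.5%.
- Exposed among non-NAFLD: (0.90 × 0.25 + 0.62 × 0.08) / 1.52 = 18.1%.
- Gap: about 6.5 percentage points. Multiplied by 0.5–1.5 SD, this is a spurious difference of 0.03–0.10 SD.
- With a standard error of 0.231 SD, the per-test type I error rises from 5% to about 7% at most.

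In this example exposure within each age band is the same with and without NAFLD, so a within-age comparison removes the imbalance without any medication record.

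**5. Bias beyond age.** A 20-point gap with a 1.5 SD shift would give 0.30 SD and a per-test type I error of about 25%. Nothing in the documents suggests a gap of that size; it marks the far end of the range.

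**The case against.** The strongest reply has four parts.

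- **Size.** Every exposure rate and effect size above is assumed. A reader might infer that the microbial signature will be distorted. The documents do not support that: they support a risk of unknown size, and evenly spread exposure mainly adds noise. This stands.
- **Recoverability.** A reader might infer that any resulting bias is beyond repair. That is too strong. Imbalance that arises only through age can be removed by comparing within age groups, which the plan already contemplates. This stands in part: the stratification is conditional on NAFLD events, sits in the fructose–NAFLD section and is not repeated for the microbiota analyses. It would also leave the noise and any imbalance within an age group.
- **Scope.** Ongoing antibiotics are captured as current therapy. The omics aim is secondary, the microbiota plan begins with exploratory work, and no power claim is made for it, so fewer effective samples contradict no stated figure. This stands, and limits the weight of the point.
- **Remedy.** Requiring stool to be postponed after an antibiotic would separate it from the same child's plasma, urine and diet recall, although metabolomics is planned on all three sample types. If use is more common in preschool children, it would also create an age-related difference in timing. This stands against a mandatory delay, but not against recording past use.

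**Conclusion.** The concern holds in a limited form. As written, the plan leaves completed antibiotic courses, and probiotics not counted as therapy, unrecorded. No later analysis can identify, exclude or adjust for those children individually. This is a gap against the protocol's own wish to protect the microbial signature.

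The consequence is possible noise and, if exposure differs by NAFLD status or fructose intake, some bias, confined to the microbiota and stool metabolome analyses. The illustrative range is a 2–47% rise in the variance of an affected feature, with the upper end combining both extreme assumptions. The age-driven example gives only 0.03–0.10 SD of spurious difference. All of this rests on assumed exposure rates and shifts.

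A reader might also infer that the main fructose–NAFLD result is at risk. It is not: stool data play no part in that comparison or in its 2.02 g figure. This is a worthwhile, inexpensive improvement to a secondary aim.

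**What to change.** 1. In the Anamnestic evaluation, extend the drug item to antibiotic and probiotic use, with agent and last date, over a look-back window that the investigators set before sampling starts. The documents offer no basis for a particular length.
2. In the Microbiota analysis section, state that beta-diversity, LEfSe and the stool metabolome analyses will be repeated without recently exposed children, or with exposure as a covariate where the method allows. The rank tests described for LEfSe take no covariate, so leaving these children out is the practical form there.
3. Report the number exposed by NAFLD group and by age group, so that any imbalance is visible.
4. Deferring the stool sample after a recent course is optional and for the investigators to decide, given the separation from plasma, urine and diet recall.

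**Cost.** One history question, some recall error, and a sensitivity analysis on a somewhat smaller sample. If 10–30% of children were set aside equally from both groups, the detectable difference in that analysis would rise from 0.65 SD to 0.68–0.77 SD (0.65 divided by √0.9 and √0.7). The main analysis on all children is unchanged.
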